## PROTOCOL SYNOPSIS

**PROTOCOL NO.:** F8394-101

**TITLE:** A Phase 1, Open-Label, 2-Part, Single Dose, Crossover Study to Examine the Effect of Food and Cobicistat Administration on the Pharmacokinetics and Safety of Plixorafenib in Healthy Participants

**STUDY PHASE:** 1

**STUDY SITE:** 1 clinical site in the United States

### **OBJECTIVES:**

#### **PART A**

The primary objectives for Part A of the study are as follows:

- To examine the effect of food on the single dose PK of plixorafenib administered with cobicistat.
- To examine the effect of cobicistat administration on the single dose PK of plixorafenib.
- To determine the safety of plixorafenib administered alone and with cobicistat in a single dose regimen in healthy participants.

The secondary objectives for Part A of the study are as follows:

- To characterize metabolites of plixorafenib in plasma and urine.
- To characterize the urinary excretion of plixorafenib.

The exploratory objective for Part A of the study is as follows:

- To examine the possible effect of pharmacogenomic variations on the PK of plixorafenib and/or the effect of cobicistat, including polymorphisms in P-gp, BCRP, and UGT.

#### **PART B**

Part A of this study demonstrated that co-administration of plixorafenib and cobicistat with a high fat, high caloric meal resulted in about 2-fold increase in average  $C_{max}$  and about 3-fold increase in average  $AUC_{0-\infty}$ , as compared to the fasted state. Since the target oncology patient population may not be able to consume high-fat and/or high-calorie meals, the effect of a low-fat meal (400 to 500 calories, with 25% from fat) and a high-fat meal (800 to 1000 calories, with  $\geq 50\%$  from fat) on the exposure of plixorafenib will be examined in Part B of this study, compared to the fasted state.

The primary objectives for Part B of the study are:

- To examine the effect of a high-fat and a low-fat meal versus fasted state on the single dose PK of plixorafenib administered alone.
- To examine the effect of a low-fat meal versus fasted state on the single dose PK of plixorafenib administered with cobicistat.
- To determine the safety of plixorafenib administered alone or with cobicistat (low-fat meal only) in a single dose regimen.

The exploratory objectives for Part B of the study are as follows:

- To examine the possible effects of pharmacogenomic variations on the PK of plixorafenib and/or the effect of cobicistat, including polymorphisms in P-gp, BCRP, and UGT.
- The effect of single dose administration of plixorifenib on endogenous biomarkers such as coproporphyrin may be evaluated.

#### STUDY DESIGN:

This is a Phase 1, open-label, 2-part, single dose, crossover, single-center study.

#### Part A

Part A is an open-label, randomized, single dose, 3-treatment, 3-period, crossover study designed to assess the effect of food and cobicistat administration on the PK and safety of plixorafenib in 12 healthy adult participants.

The study will consist of a screening period, 1 check-in, 3 treatment periods (with a 7-day washout between dosing in each period), and an EOS visit as illustrated in the table below:

Treatment Period	Screening	Check-in	Dosing	Confinement
1	Day -28 to -1	Day -1	Day 1	Day -1 to Day 19 (EOS)
2	N/A	N/A	Day 8	
3	N/A	N/A	Day 15	

N/A, not applicable; EOS, end of study.

There will be a 7-day washout between dosing in each treatment period.

EOS visit will be conducted on Day 19.

A screening evaluation will be performed to determine each participant's eligibility for the study approximately 28 to 1 days before the first dose. Participants eligible for participation will report to the study facility 1 day before dosing in Treatment Period 1 for check-in.

On Day 1 of Treatment Period 1, eligible participants will be randomized to 1 of 6 treatment sequences: 1:2:3, 2:3:1, 3:2:1, 2:1:3, 3:1:2, 1:3:2. On the first day of each treatment period, each participant will receive one of the following treatments according to the sequence in which he or she is randomized:

- Treatment 1: 900 mg plixorafenib administered after overnight fast (fasted state).
- Treatment 2: 900 mg plixorafenib + 150 mg cobicistat administered after overnight fast (fasted state).
- Treatment 3: 900 mg plixorafenib + 150 mg cobicistat administered following a high fat, high caloric meal (fed state).

For Treatment 2 and Treatment 3, plixorafenib and cobicistat will be co-administered.

All participants will fast overnight (nothing to eat or drink except water) for at least 10 hours. Participants receiving Treatments 1 and 2 (fasted condition) will continue to fast for at least 4 hours after dosing.

Participants receiving Treatment 3 will receive a standard high fat ( $\geq 50\%$  of the total caloric content of the meal), high caloric meal (approximately 800 to 1000 calories) for breakfast before dosing and this meal should derive approximately 150, 250, and 500 to 600 calories from protein, carbohydrate, and fat, respectively. Participants must consume the entire meal within

30 minutes of serving; the percentage of meal consumed will be documented. Dosing must occur 30 minutes ( $\pm$  5 minutes) after the start of the meal. Participants receiving Treatment 3 will receive their next meal no less than 4 hours after dosing.

All study drugs will be administered orally with approximately 240 mL of room temperature water. Water (except water provided with each dosing) will be restricted 1 hour prior to and 1 hour after each study drug administration, except for consuming any fluid (ie, water, milk, juice) provided with the predose meal (treatment 3 only), but will be allowed ad libitum at all other times. Up to an additional 240 mL of water will be allowed, if necessary, to aid in swallowing the study drugs when both study drugs are administered simultaneously.

Participants will remain at the facility from check-in (Day -1) to EOS and would be able to leave the facility upon satisfactory safety review. During confinement periods, participants will receive standardized meals per the clinic's standard procedures that are scheduled at the same time in each period of the study. Participants will be discharged from the study on Day 19 (Treatment Period 3).

The duration of the study for each participant, excluding screening, will be approximately 20 days. Including screening, the total study duration for each participant will be 48 days.

## Part B

Part B is an open-label, randomized, single dose, 4-treatment, 3-period, crossover study designed to assess the effect of food (either a high-fat meal or a low-fat meal) on the PK and safety of plixorafenib administered alone or with cobicistat (low-fat meal only) in 16 healthy adult participants.

This part will consist of a screening period, 1 check-in, 3 treatment periods (with a 7-day washout between dosing in each period), and an EOS visit as illustrated in the table below:

Treatment Period	Screening	Check-in	Dosing	Confinement
1	Day -28 to -1	Day -1	Day 1	Day -1 to Day 19 (EOS)
2	N/A	N/A	Day 8	
3	N/A	N/A	Day 15	

N/A, not applicable; EOS, end of study.

There will be a 7-day washout between dosing in each treatment period. EOS visit will be conducted on Day 19.

A screening evaluation will be performed to determine each participant's eligibility for the study approximately 28 to 1 days before the first dose. Participants eligible for participation will report to the study facility 1 day before dosing in Treatment Period 1 for check-in.

On Day 1 of Treatment Period 1, eligible participants will be randomized to 1 of 4 treatment sequences: A:C:D, B:D:A, D:B:C, C:A:B. On the first day of each treatment period, each participant will receive one of the following treatments according to the sequence in which he or she is randomized:

- Treatment A: 900 mg plixorafenib administered after overnight fast (fasted state).
- Treatment B: 900 mg plixorafenib administered following a high-fat high caloric meal (fed state-high fat meal).
- Treatment C: 900 mg plixorafenib administered following a low-fat meal (fed state-low-fat meal).

- d) Treatment D: 900 mg plixorafenib administered with 150 mg cobicistat following a low-fat meal (fed state-low-fat meal).

All participants will fast overnight (nothing to eat or drink except water) for at least 10 hours.

- Participants receiving Treatment A (fasted condition) will continue to fast for at least 4 hours after dosing.
- Participants receiving Treatment B will receive a high fat ( $\geq 50\%$  of the total caloric content of the meal), high caloric meal (approximately 800 to 1000 calories) for breakfast before dosing and this meal should derive approximately 150, 250, and 500 to 600 calories from protein, carbohydrate, and fat, respectively.
- Participants receiving Treatments C and D will receive a low-fat meal (approximately 400 to 500 total calories, with 25% of the total caloric content of the meal from fat) for breakfast before dosing.

All participants receiving Treatments B, C, or D must consume the entire meal within 30 minutes of serving; the percentage of meal consumed will be documented. Dosing must occur 30 minutes ( $\pm 5$  minutes) after the start of the meal. Participants receiving Treatments B, C, and D will receive their next meal no less than 4 hours after dosing.

Plixorafenib will be administered orally with approximately 240 mL of room temperature water. Water (except water provided with each dosing) will be restricted 1 hour before and 1 hour after each study drug administration, except for consuming any fluid (eg, water, milk, juice) provided with the predose meal (Treatments B, C, and D) but will not be limited at other times. Up to an additional 240 mL of water will be allowed, if necessary, to aid in swallowing the study drugs when administered with cobicistat (Treatment D).

Participants will remain at the facility from check-in (Day -1) to EOS and would be able to leave the facility upon satisfactory safety review by the investigator. During confinement periods, participants will receive standardized meals per the clinic's standard procedures that are scheduled at the same time in each period of the study. Participants will be discharged from the study on Day 19 (Treatment Period 3).

The duration of the study for each participant, excluding screening, will be approximately 20 days. Including screening, the total study duration for each participant will be 48 days.

## STUDY POPULATION:

### Inclusion Criteria:

Each participant must meet all the following criteria to be enrolled in this study:

1. The participant is able to provide written informed consent.
2. Healthy male or non-pregnant, non-lactating female participants aged 18 to 55 years, inclusive, with a BMI of  $18 \text{ kg/m}^2$  or greater, but less than  $30 \text{ kg/m}^2$ . The participant is considered by the investigator to be in good general health status as determined by physical examination, vital signs, temperature, medical history, no clinically significant abnormalities at investigator's discretion in laboratory and urine analyses, and with normal organ function as defined below:
  - Normal renal function: creatinine clearance  $\geq 90 \text{ mL/min}$ .
  - Normal liver enzymes and bilirubin ( $\leq \text{ULN}$ ).

- ECG, with QTcF interval  $\leq 450$  msec; at screening.
3. Healthy female participants must be:
    - a) Documented to be surgically sterile (surgical methods inclusive of hysterectomy, bilateral salpingectomy, and/or bilateral oophorectomy) or postmenopausal (amenorrhea for  $\geq 24$  months without an alternative medical cause and FSH  $\geq 30$  mIU/mL).
  4. OR
    - b) Using contraception, including 1 highly effective nonhormonal methods (eg, intrauterine device) in combination with a barrier contraception (eg, male or female condoms, diaphragm, spermicide, etc.) from start of plixorafenib administration until 30 days after the last plixorafenib administration, and having a negative serum or urine  $\beta$ -hCG pregnancy test (with a sensitivity of at least 25 mIU/mL) at screening and check-in.
  5. Male participants with female partners of childbearing potential must be sterile (confirmed by documented azoospermia 90 days after the procedure) or agree to use (from check-in until 90 days after discharge) one of the following approved methods of contraception: male condom with spermicide; sterile sexual partner (males must still agree to use condom with their surgically sterile female partner if unable to provide documentation of partner's sterility); or practice abstinence (abstinence is acceptable only as true abstinence when this is in line with the preferred and usual lifestyle of the participant, periodic abstinence won't be allowed); or use of an intrauterine device with spermicide by female sexual partner; a female condom with spermicide; a contraceptive sponge with spermicide; an intravaginal system; a diaphragm with spermicide; a cervical cap with spermicide; or oral, implantable, transdermal, or injectable contraceptives.
  6. Male participants must refrain from sperm donation and female participants must refrain from egg donation from check-in until 90 days after discharge from the study.
  7. The participant agrees to comply with all protocol requirements for the duration of the study.

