- Further details on vital signs (respiratory rate, body temperature, pulse rate, and blood pressure) measurements are provided in Section 6.2.4.

- g) ECG should be recorded at screening, predose within 2 hours on each dosing day, and at EOS. Further details on ECG recordings are provided in Section 6.2.5.
- h) Clinical laboratory testing will occur at screening, check-in, predose within 2 hours on each dosing day, 3 days from dosing (Day 4, 11, 18), and at EOS. If any concerning trends are seen during study, the investigator can order additional testing for safety on PRN basis. Further details on clinical laboratory assessments, including a complete list of assessments, are provided in Section 6.2.3.
- i) Further details are provided in Section 6.2.3.
- j) Urine pregnancy test to be done at screening. Serum pregnancy test to be done at check-in, and at EOS.
- k) Further details on dosing of study treatments are provided in Section 5.1.
- l) Further details on the collection of blood samples for PK analysis are provided in Section 6.1 and in Table 6-1.
- m) Further details on collection and reporting of AEs are provided in Section 6.2.
- n) Information regarding prior medications taken by the participant within the 30 days before signing the ICF will be recorded in the participant's eCRF. Details regarding prior and concomitant medications are provided in Section 5.5.1.

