#### **4.3.1 Lifestyle Restrictions**

The following lifestyle restrictions will be followed by the participants throughout the study until EOS:

1. Participants will abstain from alcohol for 48 hours prior to study drug administration and until the last set of laboratory evaluations at EOS.
2. Participants will abstain from smoking and drug use for the duration of the study. List of drugs that will be screened at screening and check-in are provided in Section 6.2.3 (Other analyses).
3. Foods or herbal preparations, including grapefruit juice, grapefruit/grapefruit-related citrus fruits (eg, Seville oranges, pomelos), are prohibited for the duration of the study.

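### Criterion 3b starts required female contraception at the first dose, which leaves a small pre-check-in gap for a woman who adopts a qualifying method late

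*Protocol*

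**What the plan says.** Criterion 3b reads the same in the synopsis and in Section 4.1. A woman who is neither surgically sterile nor postmenopausal must be using one highly effective nonhormonal method, with an intrauterine device as the example, together with a barrier. The period given is "from start of plixorafenib administration until 30 days after the last plixorafenib administration". She must also have negative pregnancy tests at screening and check-in.

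The surrounding dates come from the Part B design text and the schedule of events in Section 3.3.2:

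- Screening takes place "approximately 28 to 1 days before the first dose".
- "Participants will remain at the facility from check-in (Day -1) to EOS", which is Day 19.
- Doses are given on Days 1, 8 and 15.
- Pregnancy tests, note j: "Urine pregnancy test to be done at screening. Serum pregnancy test to be done at check-in, and at EOS".

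The neighbouring rules are these:

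- Exclusion 13 bars women who are pregnant, breastfeeding or planning a pregnancy. It sets no contraception date.
- Section 4.3.1 begins "The following lifestyle restrictions will be followed by the participants throughout the study until EOS" and then lists alcohol, smoking and drugs, and certain foods and herbal products. Contraception is not among them.
- Male contraception starts at check-in, and "female participants must refrain from egg donation from check-in until 90 days after discharge from the study".
- Exclusion 15 bars systemic medication for 14 days, or five half-lives if longer, before study drug. It makes no exception for hormonal contraceptives.

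The SAP repeats the test schedule and says nothing on contraception.

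**The concern.** The contraception rule and the Day -1 test should work together: the test excludes a pregnancy old enough to detect, and the rule prevents one too recent to detect. As dated, the rule begins after the interval that the test cannot clear. By Day 1 the participant is already in the clinic, so the stated window first matters in practice after discharge on Day 19.

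The woman at issue has no qualifying method until shortly before dosing. The protocol supplies a plausible route to this. A user of a systemic hormonal method must stop it at least 14 days before study drug under exclusion 15, and the period stated in 3b does not call for the nonhormonal replacement until Day 1. If she conceived just before check-in, she could test negative on Day -1 and meet the dated requirement. She could then receive up to three doses before the next scheduled test. What is at stake is participant safety and clear eligibility wording, not any PK comparison.

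**Working it through.** The plan gives no figure to reproduce. The check lines up dates.

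**Inputs from the documents.** Screening from Day -28; confinement from Day -1 to Day 19; doses on Days 1, 8 and 15; pregnancy tests at screening, Day -1 and Day 19; required contraception from Day 1 until 30 days after the last dose, so to Day 45 (15 + 30). There is no Day 0, by the study-day rule in SAP Section 4.

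**Input assumed.** The test turns positive L days after conception, with L = 7, 10 or 14. The documents give no detection lag.

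**Step 1, days without a stated rule.** Day -28 to Day -2 is up to 27 unconfined days, and the stated window includes none of them.

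**Step 2, days that the Day -1 test cannot clear.** A conception on Day -k is k - 1 days old on Day -1. It is missed if k - 1 < L, that is, if k ≤ L. Unconfined days have k ≥ 2. The number of missed unconfined days is therefore L - 1.

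**Step 3, age at the next scheduled test.** From Day -k to Day 19 is (k - 1) + 19 = k + 18 days.

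| Assumed lag L | Missed unconfined days | Count | Age on Day 19 (days) |
|---|---|---|---|
| 7 | Day -7 to Day -2 | 6 | 20 to 25 |
| 10 | Day -10 to Day -2 | 9 | 20 to 28 |
| 14 | Day -14 to Day -2 | 13 | 20 to 32 |

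**Step 4, exposure before Day 19.** Up to 3 × 900 mg = 2700 mg plixorafenib. Cobicistat is given once in three of the four Part B sequences (A:C:D, B:D:A and D:B:C).

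**Step 5, effect of other start dates.** If cover begins on Day -s, the uncovered conception days are those with max(s + 1, 2) ≤ k ≤ L.

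| Start of cover | L = 7 | L = 10 | L = 14 |
|---|---|---|---|
| First dose (as now) | 6 | 9 | 13 |
| Check-in, Day -1 | 6 | 9 | 13 |
| Screening, if held on Day -7 | 0 | 3 | 7 |
| 14 days before first dose | 0 | 0 | 0 |

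The last row counts by day of conception. Conception can follow intercourse by some days, and the lag is itself assumed, so the zeros show a reduction and not a guarantee.

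**The case against.** The strongest reply is that 3b is an eligibility test, phrased as something the woman is already doing. Its example is an intrauterine device, and the schedule has eligibility checked at screening and again on Day -1. A device is unlikely to be fitted during confinement, so in practice it would be in place by check-in. This stands, and it is why the gap is confined to late adopters. A reader might infer that women generally enter without contraceptive cover, and the documents do not support that. What the reply does not settle is how long before check-in the method must have been in use. The only dates given start at dosing.

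Three further inferences go too far:

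- That the later female start, compared with the male and egg-donation rules, is itself the fault. A check-in start would recover no unconfined day, as Step 5 shows.
- That nothing can intervene before Day 19. The investigator may exclude an unsuitable woman (exclusion 5), order extra safety tests (Section 6.2.3) or withdraw a participant who develops an excluded condition (Section 4.4.1). These are discretionary and set no earlier contraception date, but they exist.
- That fetal harm is shown. The protocol reports no reproductive toxicity result and describes the genotoxicity studies as negative. The Investigator's Brochure may say more and was not available.

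The consent text was not available either and could contain instructions given at screening.

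**Conclusion.** The point holds in a narrow form. The period stated in 3b begins too late to protect the interval that the Day -1 test cannot clear, and no other rule in the protocol or SAP sets an earlier start. The consequence is limited to a woman whose qualifying method begins shortly before dosing.

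The 6 to 13 days rest wholly on the assumed lag of 7 to 14 days. They describe a window and do not estimate a risk. Part A results are already reported, so the practical scope is Part B, with 16 participants, men included; the number of women affected is probably very small. Severity is minor and the change optional.

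**What to change.** In criterion 3b, in both the synopsis and Section 4.1, replace the start of the stated period. Require the highly effective nonhormonal method to be in use from screening and for at least 14 days before the first plixorafenib dose. Keep the device-plus-barrier requirement from the first dose, and keep the 30-day end.

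Both conditions are needed, because a screening start alone leaves days uncovered when screening is late. An earlier barrier step at check-in is unnecessary, since Day -1 is already confined. A pre-dose abstinence route would not fit the device requirement that applies from Day 1.

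A woman with a device in place for 14 days stays eligible even if screened late. One screened on or before Day -14 can comply going forward.

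The cost is one clause amended in two places, with the consent text aligned if needed and no added visit or test. A few women without a qualifying method in that interval would be ineligible or dosed later. The change reduces the gap but cannot be promised to close it.

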**Exclusion Criteria:**

Participants meeting any of the following criteria will be excluded from the study:

1. The participant has a history of clinically significant drug allergy or anaphylaxis, including known hypersensitivity to any components of plixorafenib or cobicistat.
2. The participant has a history of any condition(s) or gastrointestinal surgeries, including gallbladder procedures, which might affect drug absorption, metabolism, or excretion.
3. The participant has clinical evidence or a history of clinically significant cardiovascular, respiratory, renal, hepatic, gastrointestinal, hematological, neurologic, or other chronic disease as judged by the investigator.
4. The participant has a history of psychiatric disease, a suicidal attempt, hospitalization for psychiatric disease, a period of disability due to a psychiatric disease, or administers treatment to control the condition. Psychiatric disease includes major depression, bipolar disorder, or psychosis for  $\geq 3$  months.
5. The participant has a history or other evidence of illness, test abnormalities, or any other conditions which would make the participant, in the opinion of the investigator, unsuitable for the study.

6. The participant has any history of alcoholism or drug abuse, or excessive alcohol consumption (regular alcohol intake >21 units per week for male participants and >14 units of alcohol per week for female participants) (1 unit is equal to approximately ½ pint [200 mL] of beer, 1 small glass [100 mL] of wine, or 1 measure [25 mL] of spirits) within 3 months before screening.
7. The participant has positive results on screen for drugs of abuse or alcohol (Section 6.2.3 [Other analyses]) at screening visit or Day -1.
8. The participant is a smoker or has used nicotine or nicotine-containing products (eg, snuff, nicotine pouch (eg, ZYN), nicotine patch, nicotine chewing gum, mock cigarettes, vape cigarette alternatives, or inhalers), marijuana, and cannabinoids within 1 year before the first dose of study drug.
9. The participant has donated blood in the past 90 days prior to screening or has poor peripheral venous access.
10. The participant has a diagnosis of chronic or acute liver disease, for example, auto-immune, alcoholic, or neoplastic liver disease.
11. The participant has positive serostatus for HIV, HCV, or HBV.
12. Male partners of females who are pregnant.
13. Female participant of childbearing potential who is pregnant, lactating, or planning to become pregnant within 90 days after the last dose of study drug.
14. The participant has received an investigational drug, biologic, or device within 3 months or 5 half-lives of the investigational drug (whichever is longer), before receiving study drug.
15. The participant has used any systemic medications, including vitamins and over-the-counter items, during the 14 days (or 5 times the elimination half-life of the medication, whichever is longer) before receiving study drug or will require their use during the study. Inducers and inhibitors of metabolic enzymes and/or transporters (in particular CYP3A inhibitors or inducers, P-gp, and BCRP), and herbal preparations, nutritional supplements (eg, St. John's Wort), or foods, including grapefruit juice, grapefruit/grapefruit-related citrus fruits (eg, Seville oranges, pomelos), which have been shown to produce metabolic enzyme or transporter induction or inhibition, are prohibited before 5 half-lives of the investigational drug prior to check-in (Day -1). Paracetamol ≤3000 mg/day will be allowed up to 2 consecutive days before dosing and during the outpatient phase of the study, as needed.
16. The participant has been on a diet incompatible with the on-study diet, in the opinion of the investigator or designee, within 30 days prior to the first dosing and throughout the study.
17. The participant is part of the clinical staff personnel or a family member of the clinical site staff.

